6.7.2 Screening and confirmation of inclusion/exclusion criteria

Patient eligibility is checked by a clinician in the Direct Care Team at the time of surgery listing or through reviewing of the existing surgical waiting list. Their eligibility is confirmed by a member of the site Research Team prior to the patient providing informed consent at either their Surgical Consenting Clinic or Pre-Operative Assessment. This is also reconfirmed at the pre-operative MDT a week prior to surgery.

6.7.3 Pre-operative/baseline time point

Patient seen in clinic by site Research Team to discuss trial and provide informed consent.

Demographic data to be collected:

- Name
- Date of birth
- Sex of patient
- Height (cm)
- Weight (kg)
- BMI

Participant contact details to be collected and preference of communication e.g. telephone, email, post.

PROMs data to be collected for:

- OHS
- LEFS
- EQ-5D-5L

Physical activity monitor and instructions to be issued for participant to wear for two consecutive weeks, and a prepaid returns envelope provided. All activity monitors will be returned to the Hip Office, Princess Elizabeth Orthopaedic Centre at the RDE and collected periodically by the Co-CI to download the data.

Collect blood sample to measure CK and CRP biomarkers.

Ethnicity and details of any existing comorbidities to be collected from the medical notes.

Randomisation to allocated treatment arm via REDCap; site Research Team to be informed within 7 days prior to surgery; surgeon to be informed within 24 hours of surgery.

6.7.4 Peri-operative time point

- Retrospective data collection from participant medical notes review on EPIC and subsequent entry into REDCap for:
- Surgery time this will be defined from the time that surgical incision was made through to time that the wound dressing was applied at the end of the surgical procedure
- Blood loss this will be an estimate of blood loss (mls) made by the surgical and anaesthetic teams
- If there has been a conversion from allocated randomised approach this will be documented and the reason for conversion also documented

Report any AEs/SAEs that have occurred during surgery.

6.7.5 Day 0/1 post-operative time point (inpatient)

Participant seen on ward by either a member of the site Research Team (if surgery performed at RDE) or qualified Healthcare Professional (if surgery performed at Nightingale Hospital Exeter (NGE) to collect blood sample to measure CK and CRP biomarkers.

Review of electronic patient records (EPIC) by site Research Team for AEs/SAEs that occur during inpatient stay. (EPIC is available at RDE and NGE).

Length of stay recorded upon discharge; this will be measured in terms of number of nights stayed in hospital post operatively.

6.7.6 6 weeks post-operative time point

Participant seen in routine orthopaedic Outpatient clinic by site Research Team.

PROMs data to be collected for:

- OARS
- OACS
- OHS
- LEFS
- EQ-5D-5L
- SAPS

Physical activity monitor and instructions to be issued for participant to wear for 2 consecutive weeks, and a prepaid return envelope provided.

Collect blood sample to measure CK and CRP biomarkers.

Record if participant has taken any additional analgesia other than the prescribed post-surgery analgesia (yes/no). If yes, note whether this was purchased over-the-counter without prescription or via GP prescription, and record details in a free text box in the eCRF. Report any AEs/SAEs that have occurred from point of surgery to 6 weeks post-operatively.

6.7.7 6 months (26 weeks) post-operative time point

Remote follow-up by ExeCTU and site Research Team.

Electronic survey invitations for PROMs will be sent to participants directly from ExeCTU:

- OHS
- LEFS
- EQ-5D-5L
- SAPS

Participants who have opted for paper PROMs will have these posted to them by the site into REDCap by the blinded members of the site Research Team.

Physical activity monitor and instructions to be issued via post for participant to wear for two consecutive weeks, and a prepaid return envelope provided.

Report any AE/SAEs, and document any additional surgical procedures that have occurred within 6 to 26 weeks post-operatively; this is done via telephone call or email to participant. Participant will be reminded to return activity monitor. Medical notes also to be reviewed for any SAEs.

6.7.8 12 months (52 weeks) post-operative time point

Remote follow-up by ExeCTU and site Research Team.

Electronic survey invitations for PROMs will be sent to participants directly from ExeCTU:

• OHS

- LEFS
- EQ-5D-5L
- SAPS

Participants who have opted for paper PROMs will have these posted to them by the site Research Team, with a prepaid return envelope provided.

Physical activity monitor and instructions to be issued via post for participant to wear for 2 consecutive weeks, and a prepaid return envelope provided.

Report any AE/SAEs, and document any additional surgical procedures that have occurred within 26 to 52 weeks post-operative; this is done via telephone call or email to participant. Participant will be reminded to return activity monitor. Medical notes also to be reviewed for any SAEs.

6.8 Withdrawal and change to participation status

Participants have the right to withdraw at any time during the trial without prejudice to their clinical care and there is no obligation to provide reasons for withdrawal. At the time of providing informed consent, participants must be made aware that they need to contact the site Research Team should they no longer wish to participate in the trial. For each withdrawal or change in participation status, the withdrawal log on REDCap is to be completed by a member of the site Research Team, which will trigger a notification to the Trial Manager that a participant has been withdrawn, and the reason why (if provided).

Participants will be able to flexibly change their participation in the trial by selectively reducing or ceasing any or all of the following aspects:

- Use of the physical activity monitor at any time point, pre- and post-operatively
- Collection of blood biomarkers at any point pre- and post-operatively
- Completion of PROMs data at any time point, pre- and post-operatively
- Passive data collection from routine medical records (except where required for reporting of serious adverse events or for monitoring purposes)

In the event of a withdrawal or change of participation status, any available details for the reason of withdrawal should be documented in the participant's medical notes, in the eCRF, and in the investigator site file. Clarification on the nature of withdrawal of consent, as outlined above, should be sought. Allowing flexibility in participation status will protect the rights and wellbeing of the participants while maximising the opportunity to collect important outcome data and limit research waste.

If a participant withdraws their consent prior to randomisation, or if excluded on the grounds of ineligibility post-consent but prior to randomisation, they will be withdrawn from the trial (i.e. no further data collection); the data collected up until the point of withdrawal will still be available for use in trial reporting. The site Research Team will endeavour to replace such participants.

If a participant wishes to withdraw post-randomisation and prior to surgery, then the participant would either receive standard THR or withdraw from THR entirely. Participants who withdraw at this stage will not be replaced and follow-up data will not be collected.

At the discretion of the CI, participants may be withdrawn from randomised surgery and/or from follow-up data collection if it is felt in their best interest to do so. Prior to surgery, if other surgeons have an opinion that participants need to be withdrawn from randomised surgery this would need to be discussed with the CI prior to the CI making a final decision on withdrawal.

For randomised participants, all data collected up to the point of change in their participation status or withdrawal will be retained and used in the analysis. Participants who withdraw before randomisation will not be included in the final analysis. If the THR was not performed as scheduled

for unexpected reasons such as bed shortages, industrial action, staffing issues, participant short term medical issues (e.g. acute respiratory or urinary infections just prior to surgery) etc then the participant's' surgery would be rescheduled to the next available appropriate time as close as possible to the original surgical date.

For individuals who have provided informed consent, but who later lose capacity during the trial the following process will apply; the consent obtained prior to loss of capacity will not endure the loss. The participant will stop their participation but data already collected up to the point of loss of capacity will be retained and will be used in analysis.

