3 AIMS, OBJECTIVES AND OUTCOMES MEASURES

The primary aim of this trial is to investigate whether two novel robotic-assisted tendon-sparing posterior approaches (PSPA and SPAIRE) improve patient outcomes in THR compared with a robotic-assisted standard posterior approach (PA). Only patients undergoing cementless THR will be considered for the trial.

3.1 **Primary objective**

The primary objective is to determine whether there is a clinically significant between-group difference comparing PSPA vs PA, and SPAIRE vs PA for THR patients using the Oxford Arthroplasty Recovery Score (OARS) PROM at 6 weeks post-operatively, and to estimate the magnitude of any differences.

Target population	Anyone with OA of the hip requiring a total hip replacement. The trial will focus on patients suitable for a cementless acetabular component as this is appropriate for robotic guided surgery, but it will be possible to generalise the outcomes to THR procedures more generally.
Variable of interest	The primary outcome is the OARS PROM at 6 weeks post-operatively
Key intercurrent	1. Death: while alive policy: data collected up to point of death
events	2. Treatment switching: participant receives a hip replacement that is not the one they were allocated to (due to error or surgical decision at point of treatment):
	(a) treatment policy: data analysed as though intercurrent event did not occur
	(b) principal stratum: data analysed for the known subpopulation of participants who received their procedure as allocated
	3. Failure of treatment initiation: participant does not receive hip replacement at all (participant characteristics, service delivery issues):
	(a) treatment policy: cannot be applied to OARS, as only applicable post-operatively (can be applied to secondary outcomes as appropriate) (b) principal stratum: data analysed for the known subpopulation of participants who received their procedure as allocated (assumed that failure of receipt of THR would apply regardless of allocated treatment)
Population-level summary of variable	Between-group mean difference for OARS at 6 weeks post-operatively: (i) PSPA vs PA; (ii) SPAIRE vs PA

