3.4.3 PROMs

Participants will be asked to compete the following six PROMs:

- Primary outcome measure to be completed post-operatively at 6 weeks:
 OARS
- Secondary outcome measure to be completed post-operatively at 6 weeks:
 OACS
- Secondary outcome measure to be completed post-operatively at 6 weeks, 6 months (26 weeks), and 12 months (52 weeks):
 SAPS
- Secondary outcome measures to be completed pre-operatively, and post-operatively (or following scheduled date of surgery if surgery does not take place) at 6 weeks, 6 months (26 weeks), and 12 months (52 weeks):
 - \circ OHS
 - LEFS
 - EQ-5D-5L (to assess general health and quality of life)

PROMs collected pre-operatively and post-operatively at 6 weeks are to be completed by the participant during the face-to-face clinic visit with the site Research Team. PROMs collected at 6 months (26 weeks) and 12 months (52 weeks) post-operatively will be collected electronically, via survey invitations sent by ExeCTU. However, if a participant has opted to complete the PROMs on paper, these will be posted out to them at these time points by the site Research Team. The NJR has shown that the maximal improvement in pain and function post THR occurs 12 months (52 weeks) post-surgery, hence the choice of these time points for outcome assessment [31].

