8.5.2 Estimands framework

To fit with the estimands framework, a treatment policy approach will be used to deal with intercurrent events that relate to receipt of treatment, e.g. receipt of THR not as allocated, or failure to receive THR (for those outcomes that are valid in absence of THR). Deaths during the trial will be handled using the 'while alive' approach; participant data collected prior to death will be included in the analyses. In the event of death prior to 6-week follow-up, the outcome data will be deemed as 'non-existent' and will not be imputed.

As a sensitivity analysis, a principal stratum approach will be used, repeating the analysis including only those participants who received THR as allocated; these participants will be considered as 'always compliers' i.e. they will always receive treatment as allocated.

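### Section 6.8 ends all follow-up for anyone who withdraws between randomisation and surgery, including participants who go on to have a hip replacement and would still give outcome data, which does not fit the treatment-policy strategy in section 8.5.2

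*Protocol*

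**What the plan says.** Section 6.8 describes withdrawal after randomisation and before surgery. It gives two clinical outcomes, "the participant would either receive standard THR or withdraw from THR entirely", and one data rule for both: "Participants who withdraw at this stage will not be replaced and follow-up data will not be collected".

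The same section also contains three statements that treat the operation and the data separately:

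- Any participant may drop individual data streams: "Participants will be able to flexibly change their participation in the trial by selectively reducing or ceasing any or all of the following aspects". The list covers the activity monitor, blood samples, PROMs and passive collection from records.
- Staff are to establish what is being withdrawn: "Clarification on the nature of withdrawal of consent, as outlined above, should be sought".
- For withdrawal led by the chief investigator, "participants may be withdrawn from randomised surgery and/or from follow-up data collection if it is felt in their best interest". Surgery and follow-up can therefore end independently.

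On the estimand, section 8.5.2 says that "a treatment policy approach will be used to deal with intercurrent events that relate to receipt of treatment", and gives as examples a THR other than the one allocated and, for outcomes that are valid without surgery, no THR at all. In the estimand table of section 3.1, the strategy for treatment switching is "treatment policy: data analysed as though intercurrent event did not occur". The table says that treatment policy cannot be applied to OARS when no THR is received, but can be applied to secondary outcomes. Section 3.4.3 schedules OHS, LEFS and EQ-5D-5L after surgery "or following scheduled date of surgery if surgery does not take place".

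**The concern.** A treatment-policy estimand needs outcome data after the participant departs from the allocated treatment. The rule in section 6.8 stops collection at the moment of departure, whether or not the participant objects to giving data. Leaving the allocated operation is thereby turned into leaving the trial.

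Two things are at stake. First, some 6-week OARS values that could have been obtained will not exist, and they cannot be recovered later. Second, site staff cannot follow the blanket rule and the selective-participation text together, so practice may vary between participants in a way that nobody planned.

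**Working it through.** **Who is affected, and what is lost**

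| Participant withdraws before surgery and then | OARS possible? | What the estimand text expects | What section 6.8 collects | Obtainable data lost |
|---|---|---|---|---|
| has standard THR | Yes; section 3.3 excludes only those without THR | Treatment policy (8.5.2) | Nothing further | OARS, OACS, SAPS, OHS, LEFS, EQ-5D-5L, vital status |
| has no THR | No (3.1, 3.3, 8.5.3) | Treatment policy for secondary outcomes only (3.1, 8.5.2) | Nothing further | OHS, LEFS, EQ-5D-5L, vital status |
| refuses all data collection | Not obtainable | Missing data | Nothing further | None that could properly be collected |

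The conflict lies in the first two rows. Vital status is included because section 8.6.1 plans odds ratios for death to 52 weeks and section 8.6.2 applies treatment policy to death, while section 7.4 ends death reporting at withdrawal from the study.

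**Does imputation recover the loss?** Section 8.5.3 would allow missing OARS to be multiply imputed for a withdrawer who has THR, as a sensitivity analysis under missing at random. With follow-up stopped, the model has only allocation and baseline variables for that participant. For a withdrawer without THR, OARS is rightly not imputed.

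**The plan's own sample size reproduces**

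- Inputs (section 8.1): difference 10, SD 18.5, two-sided alpha 0.025, power 90%.
- Normal approximation: n = 2 × (18.5/10)² × (2.241 + 1.282)² ≈ 85 per group. The noncentral t calculation gives 87 (power 0.899 at 86 and 0.903 at 87), which is the stated figure.
- 87 / 0.85 = 102.4, so 103 per group and 309 in total.
- Revised: 321 / 3 = 107; 107 / 0.95 = 112.6, so 113 per group and 339 in total.

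None of these figures changes. They only set the scale for what follows.

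**Size of the effect**

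The protocol does not give the number withdrawing in this window. I assume 0% to 5%. Section 8.1 reports about 95% OARS completion, so 5% of 339 (about 17 people, or about 6 per arm) is roughly the loss from all causes.

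*Power.* The observed SDs are withheld to protect blinding. If the revision kept 90% power, 10 points and alpha 0.025, then 107 per group implies an SD of about 20.6.

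- If the withdrawals fall within the planned 5% loss, power is about 0.90.
- If they come on top of it, power is 0.898 (1%), 0.894 (2%), 0.891 (3%) and 0.883 (5%).

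*Shift in the mean difference.* Suppose a share r of one arm has THR but is not followed, and their mean differs by D from those kept. The observed arm mean is then off by r × D:

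| r, one arm only | D = 10 | D = 18.5 |
|---|---|---|
| 1% | 0.10 | 0.19 |
| 3% | 0.30 | 0.56 |
| 5% | 0.50 | 0.93 |

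A stress case outside this range, r = 8% and D = 15, gives 0.08 × 15 = 1.2 points. It needs about 9 of the 113 in a single arm, which is more than half of the 17 losses planned for the whole trial.

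**The case against.** The strongest defence is that the sentence concerns people who wish to withdraw, and that the protocol elsewhere (sections 6.3 and 6.8) distinguishes full withdrawal from reduced participation. On that reading the rule respects a refusal, and no estimand can demand data from someone who has refused. The principle is right, but the wording does not carry it. The preceding paragraph of section 6.8 speaks of withdrawing consent. This one speaks only of wishing to withdraw and then describes what happens to the operation. It names no consent to data collection and offers no choice.

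Several stronger readings are tempting, and the documents do not support them:

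- *That data are thrown away.* Section 6.8 keeps and analyses everything collected before withdrawal. Later data are simply not gathered.
- *That OARS is lost for everyone covered by the rule.* It is not lost for those without THR, for whom it cannot exist.
- *That these cases are exactly the treatment-switching event in section 3.1.* That entry names error or a surgical decision at the point of treatment, not participant choice. The link runs through the wider wording of section 8.5.2.
- *That section 3.4.3 is flatly contradicted.* It still applies to participants who stay in the trial but are not operated on. The conflict is limited to withdrawers without surgery.
- *That the loss is driven by allocation.* Participants are blinded, so their own wish to withdraw should not depend on their arm. Surgeons learn the allocation within 24 hours of surgery, but a surgeon-prompted withdrawal goes to the chief investigator under separate wording that already lets follow-up continue. The one-arm calculation above is therefore a deliberately unfavourable case.

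It is also fair to say that randomisation normally falls within 7 days before surgery (section 6.5), which leaves little time for withdrawal, although rescheduled participants keep their allocation and may wait longer.

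**Conclusion.** The point holds as an internal inconsistency with a small likely effect. The blanket no-follow-up rule does not fit the treatment-policy strategy in section 8.5.2, nor the selective-participation and clarification text beside it in section 6.8. The clearest consequence is the uncollected 6-week OARS of a participant who withdraws and then has standard THR. For withdrawers without THR, only secondary outcomes and vital status are affected.

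Under the assumed range of 0% to 5%, power stays between 0.88 and 0.90 and the shift stays under about 1 point against a 10-point target. That rests on an assumed withdrawal rate, an assumed score deficit and an SD inferred from the revised sample size. A reader might infer that the primary comparison is seriously compromised; nothing in the protocol shows losses large or one-sided enough for that. This is a should-fix item, justified by the contradiction and by the fact that uncollected 6-week data cannot be retrieved.

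**What to change.** In section 6.8, replace the no-follow-up sentence with wording such as: *Withdrawal from the allocated surgery is not withdrawal from follow-up; follow-up stops only for the elements the participant declines.* Non-replacement can stay as it is.

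Then, where the participant agrees:

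- collect OARS and OACS at 6 weeks, and SAPS at its planned times, after any THR;
- collect OHS, LEFS, EQ-5D-5L and deaths, counted from the scheduled surgery date if no THR takes place.

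In sections 3.1 and 8.5.2, state that withdrawal from allocated surgery before the operation is handled under the existing intercurrent events: THR not as allocated, or THR not received. Participants who refuse all data collection remain missing data.

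The chief investigator's best-interest discretion over follow-up should be left unchanged. It already separates surgery from data collection, and removing it would resolve no contradiction.

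The cost is a short protocol amendment, matching wording on the withdrawal log, and a few additional questionnaires. No new instrument, visit type or sample size is needed. For anyone already past the 6-week visit OARS cannot be recovered, so the number by arm should appear in the participant flow under section 8.3.

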- If a patient has not yet been listed for THR surgery, the trial can be introduced to them by their clinician during their routine Outpatient Assessment Clinic, once the clinician has reviewed and assessed the patient against the trial inclusion and exclusion criteria. The patient will be asked for permission for a member of the site Research Team to post or email a PIS to them. This is to be clearly documented by the clinician on EPIC.

The site Research Team will schedule a phone call to the patient within 2 weeks of sending the PIS to see if they have read and understood it, if they are interested in taking part in the trial and to answer any questions the patient might have. If the patient is agreeable, a member of the site Research Team will arrange to meet them to discuss the trial further at either their routine Surgical Consenting Clinic or Pre-Operative Assessment appointment, and take informed consent to the trial should the patient agree to participate.

Final confirmation as to whether the surgical interventions involved in the trial are appropriate to the participant will be made at the regular hip Multidisciplinary Team meeting (MDT) in the week prior to surgery. If the participant is deemed unsuitable for the trial intervention(s), they will be informed by phone to discuss this and will be withdrawn from the trial (see section 6.8). If the participant is deemed suitable, they will continue to the randomisation stage. A withdrawal for clinical reasons such as this is felt to be unlikely but may be due to rapid deterioration in the hip osteoarthritis which may deem more complex reconstruction of the hip to be required rendering the participant no longer eligible for the study.

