Participants will be randomised via REDCap within 7 days prior to surgery. Randomisations will be performed, so far as is practically feasible, in strict order by date of scheduled surgery; if more than one participant is scheduled for surgery on the same date, the participants will be randomised in order of age (older age randomised first); if there is more than one participant with the same date of birth they will be randomised in alphabetical order of surname. The member of the site Research Team performing the randomisation will be unaware of previous allocations. If any cases are scheduled at short notice, for various clinical or administrative reasons, then randomisation will be performed as close to 7 days prior to their date of surgery as possible, although this may result in randomisations being performed out of order by date of scheduling. The surgeon and theatre team will still be informed within 24 hours of surgery. If a patient has surgery rescheduled after they have been randomised within 7 days prior to surgery (usually to last minute urgent or trauma cases), their randomisation will be retained. The patient's surgery will be rescheduled for as close as possible to their original date and surgeon/clinical team informed of the randomisation group within 24 hours prior to surgery. The Research Coordinator, Senior Trials Administrator and Team Lead at site will be unblinded and they will be notified of randomised allocation directly from REDCap immediately on randomisation being performed, within 7 days prior to surgery. The operating surgeon and allocated members of theatre staff will be notified of the randomised allocation directly from REDCap within 24 hours prior to surgery. This schedule for randomisation is intended to minimise post-randomisation attrition. Please refer to Table 1 in section 6.6 for summary.

In the event that a participant has been randomised and their planned surgery does not go ahead or they change their mind about participating in the trial, the site Research Team will notify the Trial Manager immediately.

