6.6 Blinding

The trial will be double-blinded; the participants will be unaware of which type of surgical approach they have received, and identified members of the site Research Team, which will include the Research Nurse and Research Practitioners who collect outcome data, will also be blinded to the allocated group. Surgeons will remain blinded until the randomisation email is received within **24 hours of surgery**. Operating surgeons will not be involved in collecting any post-operative data. A Senior Statistician will be unblinded throughout the trial to facilitate provision of unblinded reports to the DMC. Blinding of the analysing statistician will be considered, using the Blinding of Trial Statisticians (BOTS) guidance [32]. Use of the BOTS tool will allow a more thorough understanding

of the risks of unblinding of the analysing statistician. However, the default position for the trial will be that the trial statistician (performing data analysis) will remain blinded until the presentation of the primary analyses of the primary and secondary outcome data. At this point, the wider trial team will be unblinded. The remaining analyses will then be performed with the statistician unblinded. Any deviation from this position will be made in the light of the risk assessment derived from the BOTS tool. The Research Coordinator, Senior Trial Administrator and, by means of contingency, the Research Team Lead, will be unblinded and will randomise participants via REDCap within **7 days prior to surgery**; they will also enter the surgical data to the trial database. Post-operative care does not differ between each technique, and the surgical dressing is applied to the same site over the hip area and cannot be distinguished between each approach. The documentation about the surgical approach in the operation notes will not specify which technique was used for the procedure and will state that the patient is enrolled in the HIPSTER research trial. Table 1 below summarises the planned blinding status for key personnel.

BLINDED	Notified of treatment allocation when?	How?
	At end of trial (as defined in	Via letter from site
Participants	section 6.11), if requested.	Research Team
Site Research Team* (co- ordinating follow-ups)		
	Up to 24 hours prior to	
Surgeon	surgery	Automatically via REDCap

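### Section 6.8 lets a randomised participant be withdrawn from allocated surgery, from follow-up, or from both, after the surgeon has learned the arm, so loss of OARS can depend on allocation

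*Protocol*

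**What the plan says.** All references are to the protocol.

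- **Suitability comes first.** Section 6.1 assigns the last suitability check to the MDT, in the week before surgery: "Final confirmation as to whether the surgical interventions involved in the trial are appropriate to the participant will be made". It places randomisation after that check: "If the participant is deemed suitable, they will continue to the randomisation stage". Section 6.7.2 says of eligibility: "This is also reconfirmed at the pre-operative MDT a week prior to surgery".
- **Surgeons are blind at that stage.** Section 6.6: "Surgeons will remain blinded until the randomisation email is received within" 24 hours of surgery. It adds that the arm is not discussed at the MDT.
- **Withdrawal stays open afterwards.** Section 6.8 gives the CI discretion: "participants may be withdrawn from randomised surgery and/or from follow-up data collection if it is felt in their best interest". Before surgery, "if other surgeons have an opinion that participants need to be withdrawn from randomised surgery this would need to be discussed with the CI", and the CI decides.
- **Rescheduling.** Section 6.5 begins a rule with "If a patient has surgery rescheduled after they have been randomised within 7 days prior to surgery" and keeps the existing allocation.
- **Analysis.** Under sections 3.1.1 and 8.5.2 the main analysis uses a treatment policy approach to switching. A principal stratum sensitivity analysis keeps only those treated as allocated and regards them as always-compliers. Section 3.1.1 also assumes that failure to receive a THR would have occurred whatever the allocation. OARS cannot be completed, and is not imputed, without a THR (3.3, 8.5.3).

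**The concern.** The order of events in 6.1 and 6.6 is sound: suitability is decided by people who cannot know the arm, and randomisation follows. Section 6.8 leaves a discretionary route open past that point. It sets a best-interest criterion. It does not require the request to precede disclosure, and it does not require the person deciding to be unaware of the arm. The phrase about other surgeons implies that the CI is a surgeon too.

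The incentive to use this route need not be equal across arms. Sections 5.4 and 5.5 describe PSPA and SPAIRE as restricting access and making cup positioning harder, and section 1 calls SPAIRE the more demanding of the two. A hip that looks difficult the day before surgery is a more natural reason to take someone out of a tendon-sparing allocation than out of PA. If such people also leave follow-up or have no THR, the arms compared on OARS are no longer the arms that were randomised. A larger sample would not correct that.

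**Working it through.** **1. Who knows what, and when.**

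| Step | Section | Operating surgeon knows the arm? | Can the participant leave the trial or the allocated surgery? |
|---|---|---|---|
| MDT, week before surgery | 6.1, 6.6, 6.7.2 | No | Yes, before randomisation |
| Randomised, more than 24 hours before surgery | 6.5 | No | Yes, by 6.8 discretion |
| Last 24 hours | 6.5, 6.6 | Yes | Yes, by the same discretion |

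The third row is the problem: 6.8 does not distinguish it from the second.

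**2. What each outcome does to the analyses.**

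- *Withdrawn from allocated surgery, has a THR by another approach, is followed.* OARS is observed and the participant stays in the primary analysis as randomised. They leave the principal stratum analysis.
- *Withdrawn from allocated surgery and from follow-up.* OARS is missing from the primary analysis. Multiple imputation is a sensitivity analysis under missing at random (8.5.3), and its listed variables do not include a surgeon's view of difficulty.
- *No THR.* OARS does not exist and is not imputed. The section 3.1.1 assumption that this is independent of allocation fails if the decision used the allocation.

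**3. The trial's own figures.** Section 8.1 gives a target difference of 10 points, a planning SD of 18.5, 321 evaluable participants and a target of 339. Per arm, 321/3 = 107. Allowing 5% loss, 107/0.95 = 112.6, rounded up to 113, and 3 × 113 = 339. This reproduces the stated target and is not in dispute.

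**4. Size of a possible bias.** The protocol gives no rate for this kind of withdrawal, so the inputs are assumptions. Let a fraction x of one arm lose OARS in this way, with a mean g points below the full-arm mean, and let no such loss occur in the comparator. The mean of those remaining rises by x·g/(1 − x).

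| x (of 113) | g = 5 | g = 10 | g = 20 |
|---|---|---|---|
| 2% (about 2 people) | 0.02×5/0.98 = 0.10 | 0.20 | 0.41 |
| 5% (about 6 people) | 0.05×5/0.95 = 0.26 | 0.53 | 0.05×20/0.95 = 1.05 |

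Against the 10-point target this is about 1% to 10%. For scale, the standard error of one contrast at the planning SD is 18.5 × √(2/107) = 2.5 points. It will be somewhat larger in practice, because section 8.1 reports observed SDs above 18.5.

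**5. Plausibility of the upper end.** Section 8.1 reports about 95% completion of the primary outcome at 187 participants, so about 5% non-completion from all causes. A 5% loss by this route in both tendon-sparing arms and none in PA is (5% + 5% + 0%)/3 = 3.3% overall, about two thirds of all non-completion. The upper end is therefore demanding.

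**The case against.** The case on the other side is substantial.

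- **Withdrawal from surgery is not exclusion.** A reader might infer that anyone a surgeon takes out of randomised surgery drops out of the analysis. The text does not say so. The sentence about other surgeons covers randomised surgery only, and treatment policy retains those who have a THR and are followed. The 6.8 rule that follow-up is not collected concerns participants who themselves wish to withdraw before surgery. This stands, and it limits the point to cases where follow-up is also stopped or no THR occurs, plus the principal stratum analysis.
- **Surgeons have another option.** Sections 2 and 5.2 allow further tendons to be released during surgery. Such conversions are recorded and the participant is analysed as randomised. This makes pre-operative withdrawal less likely but does not close the route.
- **There are controls.** The CI has the final say, withdrawals are logged in REDCap with any reason given (6.8), and participant flow follows CONSORT (8.3). However, section 6.8 does not ask for a record of whether the allocation was known, which is what a reader would need.
- **Rescheduled cases.** It is tempting to read 6.1 as sending a postponed, already randomised participant through the MDT gate again, with a surgeon who knows the arm. The protocol does not state this. The 6.1 step leads into randomisation, and the arm is not discussed at the MDT. The protocol does not exclude a repeat check either, and not discussing the arm does not re-blind a surgeon already told. This supports a clarification and no more.
- **Direction.** Section 5.4 says PSPA is the approach Exeter surgeons use most, so a surgeon might equally doubt PA for a given patient. A bias that always favours tendon-sparing cannot be claimed.

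**Conclusion.** The point holds in limited form. Section 6.8 permits, by a stated rule, a withdrawal decision made with knowledge of the arm after a process designed to settle suitability without it. Through stopped follow-up or a THR that does not take place, loss of OARS can then depend on allocation. The principal stratum analysis is exposed even when follow-up is complete, because arm-aware withdrawal contradicts both the always-complier reading and the assumption that non-receipt of THR is unrelated to allocation.

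The effect on the primary contrasts is probably small: 0.1 to 1.05 OARS points if 2% to 5% of one arm is lost with a deficit of 5 to 20 points and nothing comparable happens in the comparator. None of these inputs comes from the protocol. If difficult hips are the ones removed, the bias favours the tendon-sparing arms, which is plausible but not established. The change is worth making because it is cheap and because the size cannot be checked afterwards unless disclosure status is recorded.

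**What to change.** In section 6.8:

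1. State that trial eligibility is fixed at randomisation.
2. State that a later decision not to perform the allocated approach remains a clinical decision, is logged as the treatment-switching or non-initiation event already defined in 3.1.1, and does not by itself end follow-up.
3. Limit the CI's power to stop follow-up so that withdrawal from randomised surgery does not trigger it.
4. For every such event, record the date, the reason and whether the allocation had been disclosed, and report these by arm.

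In section 6.5, state that a participant already randomised and then rescheduled does not pass through the 6.1 trial-withdrawal step again, and record whether the allocation had already been released.

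The cost is protocol wording and a few REDCap items. No visits or participants are added, and surgical care is not constrained. The small downside is that a few more participants will be followed after surgery by an approach other than the one allocated. If recruitment has closed, existing post-randomisation withdrawals can still be classified by arm, reason and timing relative to disclosure, as far as the records allow.
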